## **10. Data Analysis**

Approach: Intention-to-treat and per-protocol. Statistical tests: Repeated measures ANOVA and linear regression models (adjusted for baseline, age, BMI, running duration, symptom duration). Multiple imputation for missing data. Effect size: Partial eta squared ( $\eta^2$ ).

Significance:  $p < 0.05$ .

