## 3. Objectives

Primary Objective: To determine the effectiveness of wearable device-assisted gait retraining on pain reduction during running in female runners with PFP.

Secondary Objectives:

- To assess improvements in function (Anterior Knee Pain Scale, AKPS)
- To examine changes in running mechanics (knee kinematics, kinetics, PFJS)
- To evaluate adherence, feasibility, and safety of wearable device-assisted gait retraining

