## 4. Study Design

Type: Randomized, controlled, single-blind, parallel-group trial

Allocation: 1:1 randomization

Masking: Outcome assessors blinded; participants not blinded due to intervention nature

Arms:

- Intervention Arm: Education + Wearable device-assisted gait retraining
- Control Arm: Education only

Study Duration: 18 weeks per participant (6-week intervention + 12-week follow-up)

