## 7. Outcomes

### 7.1 Primary Outcome

Pain during running (VAS-R, 0–100 mm) at baseline, 6 weeks, and 18 weeks

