## **8. Sample Size**

Sample size estimated with G\*Power. Detectable difference: 20 mm VAS (MCID for PFP).

Power: 80%,  $\alpha = 0.05$ . Estimated: 22 participants per group (total n=44), accounting for 15% dropout.

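### No section names the visit, model or population that decides the primary VAS-R result, so the deciding test can be chosen after the data are seen

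*Combined protocol and SAP*

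**What the plan says.** All references are to the combined protocol and SAP.

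- Section 3 states the primary objective without a time point: "To determine the effectiveness of wearable device-assisted gait retraining on pain reduction during running in female runners with PFP".
- Section 4 gives the timeline: "Study Duration: 18 weeks per participant (6-week intervention + 12-week follow-up". Week 6 is therefore the end of treatment, and week 18 is 12 weeks later.
- Section 7.1 defines the primary outcome as "Pain during running (VAS-R, 0–100 mm) at baseline, 6 weeks, and 18 weeks" and ranks neither post-baseline visit.
- Section 8 sizes the trial on one difference, "Detectable difference: 20 mm VAS (MCID for PFP", at 80% power and alpha 0.05. It names no visit, test or SD. The result is "Estimated: 22 participants per group (total n=44), accounting for 15% dropout".
- Section 10 reads "Approach: Intention-to-treat and per-protocol. Statistical tests: Repeated measures ANOVA and linear regression models". The regression is adjusted for baseline and four further covariates, the threshold is p below 0.05, and the only summary of size is "Effect size: Partial eta squared". Nothing in Section 10 is labelled primary. It names no ANOVA term and no regression visit, and it gives no order of testing, no multiplicity rule and no rule for conflicting results.

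**The concern.** The two visits answer different questions: whether pain is lower when retraining ends, and whether any gain lasts. The two models and the two populations can also give different p-values from the same trial. With none of these choices fixed, the result that answers the primary objective can be selected after the data are known.

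Two things are at stake. If there is no true effect and any significant result may be claimed, the false-positive chance is above the 0.05 used to size the trial. If the treatment works, the visits or the models can fall on opposite sides of 0.05, and the plan then contains no pre-specified answer to its own primary objective.

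**Working it through.** **1. The plan's own figure.** Section 8 gives no SD, so 22 per group cannot be derived from the stated inputs alone. Back-solving for a two-sided two-sample t-test: an SD of 20.5 mm gives d = 20/20.5 = 0.98 and 18 per group, and 18/0.85 = 21.2, which rounds up to 22. The figure is attainable and corresponds to one comparison at one alpha of 0.05.

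**2. Number of available tests.** Section 10 offers two models in two populations. If regression is run at each visit, there are three VAS-R tests per population (group-by-time, week 6, week 18) and six in all. If k tests were independent, the chance of at least one false positive would be 1 − 0.95^k, which is 0.0975 for k = 2. These tests are correlated, so simulation is needed.

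**3. No true effect.** There were 20,000 simulated trials per setting, with complete data. Settings were 18, 19 or 22 analysed per arm; equal correlation between visits of 0.3, 0.5 or 0.7; and a per-protocol set losing 10, 20 or 30% at random from one arm or both. The documents give neither the correlations nor a definition of the per-protocol set, so both are assumptions. The models were:

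- Regression: VAS-R at the visit = b0 + b1·group + b2·baseline + four covariates unrelated to outcome, testing b1 = 0.
- ANOVA: the group-by-time F test over three visits, on 2 and 2(N − 2) degrees of freedom.

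| Decision rule | False-positive chance |
|---|---|
| One named ITT regression | 0.046–0.052 |
| One named ITT group-by-time test | 0.045–0.053 |
| Group-by-time in ITT or per-protocol | 0.058–0.080 |
| ITT group-by-time or ITT regression at one visit | 0.077–0.089 |
| ITT regression at either visit | 0.089–0.100 |
| Any of six tests (illustrative) | 0.130–0.184 |

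A second simulation (10,000 trials per setting, 22 per arm, correlation 0.3–0.9, per-protocol set of about 85%) gave 0.091–0.094 for regression at either visit and 0.145–0.162 for six tests. For the three ITT tests alone it gave 0.107–0.117.

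**4. True effect.** 22 × 0.85 = 18.7, so 18–19 per arm are analysed. By the noncentral t, 80% power at two-sided 0.05 needs 0.961 SD with 18 per arm and 0.934 SD with 19. With that effect at both visits, the share of trials in which the week 6 and week 18 regressions disagree is:

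| Correlation | 18 per arm | 19 per arm |
|---|---|---|
| 0.3 | 0.316 | 0.305 |
| 0.5 | 0.218 | 0.215 |
| 0.7 | 0.084 | 0.078 |

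A one-visit regression disagrees with group-by-time in 0.050–0.287 of trials. Where the visits disagree, group-by-time is significant in 0.569–0.861 of trials, but nothing in the plan says that it decides. If the week 18 effect is assumed to be half as large, the visits disagree in 0.522–0.586.

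Dropout patterns and multiple imputation were not simulated.

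**The case against.** The strongest reply is that the plan already points to one test. VAS-R is listed at three times, ITT and repeated-measures ANOVA come first, and partial eta squared is the only effect size. That fits a single ITT group-by-time test, with regression and per-protocol as the customary supportive analyses, and such a test holds about 0.05. This is a fair inference, but listing order is not designation. The omnibus term also would not say at which visit the arms differ.

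Second, every rate above 0.05 requires a rule that any significant result counts, and the plan does not state one. If all listed tests had to agree, the chance would be well under 0.01. This stands. A reader might infer that the trial has a type I error of 0.13–0.18; the documents do not support that. The range needs six chances to succeed, separate regressions at each visit (which Section 10 does not state) and assumed per-protocol losses.

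Third, if the effect fades, different results at weeks 6 and 18 are a correct finding, and naming one visit would not make them agree. This also stands. The 0.52–0.59 rests on an assumed halving and is illustrative only.

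Fourth, the 0.93–0.96 SD effect is calibrated to an unadjusted t-test. The adjusted regression then has power of about 0.77, 0.84 and 0.95 at correlations 0.3, 0.5 and 0.7, so the disagreement range mixes different power levels and its upper end applies only at the lowest correlation.

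None of these replies supplies the missing designation.

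**Conclusion.** The concern holds as a missing decision rule, not as a demonstrated error rate. No section fixes the visit, model or population for the primary result, and this should be corrected before outcome data are seen.

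If any significant result may be claimed, the false-positive chance is about 0.06–0.09 on the readings closest to the text, and about 0.09–0.10 if regression is run at each visit. One named ITT test would hold about 0.05. The direction does not depend on the assumed correlations unless the tests are perfectly correlated; the exact size does. With equal effects at both visits, an effective treatment would still leave the two visits on opposite sides of 0.05 in about 0.08–0.32 of trials, given the assumed correlations and effect size.

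**What to change.** Before data are seen, amend Sections 7.1 and 10 as follows.

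1. Name one primary test at two-sided 0.05: the ITT between-group difference in VAS-R at one named visit, adjusted for baseline and the other listed covariates.
2. Test the other visit next in fixed sequence at 0.05, only if the first is significant.
3. If an omnibus ITT group-by-time test is preferred as primary, state that it decides. Test the two visit-specific differences only if it is significant, in a stated order.
4. Label the other model and the per-protocol set as supportive.

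This is wording only, with no extra participants or data. The price is that an effect significant only at the second-ranked visit could not be claimed as confirmatory. With equal effects that happens in 0.036–0.159 of simulated trials. If the week 18 effect is half as large (assumed), it happens in 0.007–0.044 with week 6 first and 0.514–0.551 with week 18 first. The sponsor should therefore set the order by the question it most wants answered: immediate or lasting benefit.

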## 5. Participants

Inclusion Criteria:

- Female, age 18–45 years
- Unilateral/bilateral anterior knee pain > 4 weeks
- VAS pain  $\geq 3/10$  during running and  $\geq 2$  of the following: jumping, squatting, kneeling, stairs, prolonged sitting, or resisted knee extension
- Running  $\geq 15$  km per week
- Natural rearfoot striker (verified by high-speed video)

Exclusion Criteria:

- Acute trauma, history of patellar dislocation, meniscal/chondral lesions
- Prior knee surgery or injection in past 12 months
- Rheumatologic, neurologic, or degenerative disease

- Pregnancy

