## 6. Interventions

### 6.1 Control Group (Education)

Delivered via WeChat platform. Content: PFP education, load management strategies, symptom-based training modifications, and strengthening exercises (quadriceps & hip). Self-monitored running program guided by pain thresholds.

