### 6.2 Intervention Group (Gait Retraining + Education)

Same education program as control. Gait retraining protocol: 6-week program, twice per week. Step rate increased by 10%, monitored via smartwatch (Huawei GT4). Real-time cadence feedback via auditory metronome cues. Feedback frequency: every session (weeks 1–4), once (week 5), faded (week 6). Duration progressed from 15 min to 30 min per session. Pain monitoring: ≤ 3/10 during running, return to baseline within 60 min.

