### 7.3 Safety Outcomes

Adverse events (pain exacerbation, injuries, withdrawal)

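### Does naming a per-protocol analysis next to ITT, without defining or ranking it, let the VAS-R conclusion rest on a set selected for low running pain?

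*Combined protocol and SAP*

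**What the plan says.** Section 10 gives the analysis sets in one phrase, "Approach: Intention-to-treat and per-protocol". It then names repeated measures ANOVA and adjusted linear regression, multiple imputation and a single significance threshold of p < 0.05. Neither Section 10 nor any other section says who belongs to the per-protocol set, what counts as a deviation, or which set takes precedence.

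The primary outcome in Section 7.1 is "Pain during running (VAS-R, 0–100 mm) at baseline, 6 weeks, and 18 weeks". Section 6.2 gives the retraining arm a schedule, "Gait retraining protocol: 6-week program, twice per week", a smartwatch-monitored step-rate target, and a pain rule: "Pain monitoring: ≤ 3/10 during running, return to baseline within 60 min". Section 5 requires "VAS pain $\geq 3/10$ during running" for entry. Section 6.1 describes the control arm's running as "Self-monitored running program guided by pain thresholds". Section 7.3 lists pain exacerbation and withdrawal among the adverse events. Section 8 plans 22 per group with 15% dropout.

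**The concern.** Read together, these sections seem to tie protocol completion to the outcome. Every participant enters with running pain at or above the level the retraining protocol uses as its limit, and running pain is what the trial measures. If breaching the limit, or missing sessions because of pain, took a runner out of the per-protocol set, the retraining arm would lose its high-pain members. The control arm has no scheduled sessions to fall short of and might lose none. The comparison would then be selected on VAS-R in one arm and could show a benefit where none exists. Because Section 10 puts both sets under one threshold without ranking them, a favourable per-protocol result could in principle be presented as the trial's answer when ITT disagreed.

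**Working it through.** **Where the inputs come from.** The documents give 22 per group, 15% dropout and a 20 mm difference. They give no SD, exclusion share or correlation, so those are assumptions.

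**The plan's own figure.** n per group = 2(1.960 + 0.842)² × SD² / 20². With an assumed SD of 21 mm this is 17.3, rounded up to 18, and 18/0.85 = 21.2, rounded up to 22. The stated 22 is attainable, but it cannot be verified without the SD. For the check, 15% of 22 is 3.3; taking 3 lost leaves 19 evaluable per arm. An exact t-test at 19 per arm has 80% power for 20 mm at SD 21.4, and 21.3 mm is used below.

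**Size of the bias if the set were built on pain.** Assume no true effect and remove the k of 19 retraining runners with the highest session pain. With p = k/19, z the normal quantile exceeded with probability p, and φ the normal density, the standardised mean session pain of those kept is about −φ(z)/(1 − p). Let session pain and 6-week VAS-R each correlate 0.5 with baseline, and let r be their correlation with each other. Baseline adjustment then leaves

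bias ≈ SD × [−φ(z)/(1 − p)] × (r − 0.5 × 0.5).

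- k = 4: p = 0.211, z = 0.805, φ = 0.289, mean of those kept −0.366.
- k = 6: p = 0.316, z = 0.480, φ = 0.356, mean of those kept −0.520.

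Negative values favour retraining. The simulation columns come from 40,000 trials per setting with baseline-adjusted ANCOVA; error is in favour of retraining, nominal 2.5%.

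| k | r | Formula, mm | Simulated bias, mm | Simulated error |
|---|---|---|---|---|
| 4 | 0.5 | −1.95 | −1.9 | 4.8% |
| 4 | 0.7 | −3.50 | −3.5 | 7.9% |
| 6 | 0.5 | −2.77 | −2.8 | 5.9% |
| 6 | 0.7 | −4.98 | −5.0 | 11.1% |

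The arithmetic is sound, given its premises.

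**What happens when the premises move.**

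- At r = 0.25, where session pain relates to the outcome only through baseline, the bracket (r − 0.25) is zero and so is the bias.
- If the same rule removes as many controls, the bias is zero.
- If exclusions are unrelated to outcome, the bias is zero and per-protocol error is 2.5% to 2.6%. Accepting whichever set succeeds gives 3.3% to 3.6%.
- If improved runners are the ones who stop (r of −0.3 with k = 4, or −0.5 with k = 6), the bias is 2.3 to 5.3 mm against retraining.
- If every retraining runner above 30 mm is removed, with no baseline adjustment and an assumed mean of 30 mm and SD of 20 mm, about 11 of 22 leave. The false benefit is 4.8 to 14.4 mm for correlations of 0.3 to 0.9.

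The result therefore runs from zero to large and can take either sign, depending on figures the documents do not give.

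**Is ITT a clean comparator?** Only if dropout is unrelated to pain. Apply the same mechanism to dropout, so that the 3 of 22 retraining runners lost are those with the highest session pain while control dropout is random. Then p = 0.136, z = 1.097, φ = 0.219, and the mean of those kept is −0.253. The bias is 21.3 × (−0.253) × 0.25 = −1.3 mm at r = 0.5 and 21.3 × (−0.253) × 0.45 = −2.4 mm at r = 0.7. Simulated error favouring retraining is about 4% and 6%. This uses a complete-case ANCOVA as an approximation to imputing from arm and baseline. A pain-driven mechanism would therefore affect both analyses, and the gap between them is smaller than a comparison with an unbiased ITT suggests.

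**Does the text build the set on pain?** No. Section 6.2 calls the limit monitoring and does not call exceeding it a deviation; a runner who cuts a session short because of pain may be following the rule. Sections 3, 6.2 and 7.2 offer adherence, session attendance and logged cadence as criteria. Both arms receive the same education, including pain-guided running.

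**The case for a change.** The strongest opposing case does not depend on any assumed number. The primary outcome has two analyses, one of them undefined, with no stated rule for disagreement. In this trial, unlike most, the protocol being followed includes a limit on the outcome variable. Even an attendance criterion could bring pain in indirectly, because runners in pain miss sessions and only the retraining arm has sessions to miss. A few sentences would settle the matter at almost no cost.

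Most of this is accurate. The definition and the ranking are absent, selection on pain in one arm is a real possibility, and one-sided scheduling makes it plausible. What does not follow is that the plan as written leads to a wrong conclusion. The harmful reading needs three choices the text does not make: a pain-dependent set, applied unequally between the arms, and then preferred to ITT. Writing rules down would not by itself remove the risk either, since a per-protocol set defined in advance on pain-related sessions would carry the same bias.

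**Conclusion.** No change follows. The gap is one of missing detail that analysts fill sensibly: ITT is planned and named first, and in a superiority comparison it is ordinarily read as primary with per-protocol in support. A literal pain-limit criterion is also an unlikely choice here, because everyone enters at or above the limit and applying it could remove about half the retraining arm at an assumed mean session pain of 30 mm.

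The 1.9 to 5.0 mm range is correct for its assumptions: SD 21.3 mm, 4 or 6 of 19 excluded from one arm only, correlations of 0.5 to 0.7, and no true effect. None of those inputs is in the documents, and neighbouring assumptions give zero or the opposite sign, so the range illustrates a possibility and does not measure a defect. A reader of the eventual report should weigh any per-protocol result by how many were excluded from each arm and why.

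### Running pain has two follow-up visits and two models with none named primary, so the stated 5% level is not held; the only named effect size also cannot be compared with 20 mm

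*Combined protocol and SAP*

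**What the plan says.** - **Objective (Section 3).** The primary objective concerns the "effectiveness of wearable device-assisted gait retraining on pain reduction during running in female runners with PFP". This is a question about direction as well as size.
- **Visits (Sections 4 and 7.1).** The primary outcome is "Pain during running (VAS-R, 0–100 mm) at baseline, 6 weeks, and 18 weeks". Participation lasts "18 weeks per participant (6-week intervention + 12-week follow-up", so week 6 is the end of the programme and week 18 the end of follow-up. Neither is called primary.
- **Sizing (Section 8).** "Detectable difference: 20 mm VAS (MCID for PFP", with 80% power and alpha 0.05, leading to "22 participants per group (total n=44), accounting for 15% dropout". The visit at which the 20 mm should be seen is not stated, and no SD is given.
- **Analysis (Section 10).** The tests are "Repeated measures ANOVA and linear regression models (adjusted for baseline, age, BMI, running duration, symptom duration"). They stand side by side with one significance threshold, p < 0.05. The effect-size statement is "Multiple imputation for missing data. Effect size: Partial eta squared". No section mentions a between-group difference in mm, a confidence interval or a multiplicity adjustment.

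**The concern.** A single 5% test needs one outcome, one visit and one model fixed before the data are seen. Here the outcome is fixed but the visit and model are not. A positive result at week 6 only, at week 18 only, or in one of the ANOVA terms could each be presented as the primary finding without departing from the plan. The real chance of a false positive then exceeds the stated 5%.

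The second issue is how the result will be expressed. The trial is sized on a difference in mm, but the one effect measure named is a proportion of variance. It carries neither direction nor units, so it cannot by itself show whether the difference favoured gait retraining or reached 20 mm.

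**Working it through.** **Inputs.** From the documents: 22 per group, 15% dropout, two post-baseline visits, two models, p < 0.05, 20 mm. Assumed: visit correlation r of 0.3, 0.5 or 0.7 (equal between all visits), baseline as the only covariate, no missing data. Evaluable number: 22 × 0.85 = 18.7, taken as 19 per arm.

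**The plan's own sample size.** It cannot be reproduced, because no SD is given. With a two-sided t test and 18 evaluable per arm (18/0.85 = 21.2, rounded up to 22), an SD of about 20.8 mm would yield it. The false-positive figures below need no SD.

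**Step 1: regression at either visit.** With no treatment effect, each test is positive 5% of the time, so the chance of at least one is 5% + 5% − P(both), and cannot exceed 10%. After adjustment for baseline, the correlation between the week 6 and week 18 estimates is (r − r²)/(1 − r²) = r/(1 + r). P(both) is then the bivariate normal probability that both statistics lie beyond ±1.96.

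| r | r/(1 + r) | P(both) | At least one positive |
|---|---|---|---|
| 0.3 | 0.23 | 0.39% | 9.6% |
| 0.5 | 0.33 | 0.54% | 9.5% |
| 0.7 | 0.41 | 0.70% | 9.3% |

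A simulation of 40,000 null trials with 19 per arm gave 9.7 / 9.6 / 9.7%. This agrees with the table to within about half a percentage point.

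**Step 2: adding the ANOVA tests.** The same simulation counted trials with p < 0.05 in at least one of four VAS-R results: ANOVA group, ANOVA group-by-time, regression at 6 weeks, regression at 18 weeks. Section 10 does not say how baseline enters the ANOVA, so both readings were run.

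| Baseline in the ANOVA | r = 0.3 | r = 0.5 | r = 0.7 |
|---|---|---|---|
| One of the time levels | 14.5% | 14.7% | 14.8% |
| Covariate | 13.4% | 13.3% | 13.4% |

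Each single test stayed at 4.9-5.2%. The excess therefore comes from the choice among tests, not from a fault in any one of them.

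**Step 3: what partial eta squared says about 20 mm.** For a plain two-group comparison at one visit with n = 18 per arm, F = n(20/SD)²/2 and partial eta squared = F/(F + 34). The SD values are assumptions.

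| Assumed SD (mm) | F | Partial eta squared for 20 mm |
|---|---|---|
| 15 | 16.0 | 16/50 = 0.32 |
| 20 | 9.0 | 9/43 = 0.21 |
| 25 | 5.76 | 5.76/39.76 = 0.145 |
| 30 | 4.0 | 4/38 = 0.105 |

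Read the other way, a reported 0.14 would correspond to about 12, 16, 20 or 24 mm for these four SDs. The difference enters squared, so 20 mm of harm gives the same value as 20 mm of benefit.

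**The case against.** The strongest reply is that the plan already contains what is needed. VAS-R is in mm, the target is in mm, and the listed regression adjusts for baseline. If treatment group is a term, as the text implies, its coefficient is a signed difference in mm. Partial eta squared is a usual companion to ANOVA, and naming it does not forbid group means or coefficients. This stands. A reader might infer that the trial will report no mm difference, or that nobody will be able to tell which arm did better. The documents do not support that: it would be true only if partial eta squared were reported alone. What remains is that nothing makes the coefficient the headline result, fixes its visit or promises an interval.

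A second reply is that 13-15% overstates the problem. This also stands in part. It is a ceiling under free choice from a menu of four that the plan does not itself count out. It also includes results in either direction, although the objective concerns pain reduction. Counting only false claims of benefit, the either-visit figure is about half: 2.5% + 2.5%, less the 0.2-0.35% chance that both favour the intervention, or roughly 4.7% against a nominal 2.5%. The inflation is still close to twofold. The menu omits the intention-to-treat and per-protocol choice, which Section 10 also lists without ranking.

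A third reply is that the false-positive figures have nothing to do with partial eta squared. That is correct. They would be the same if the effect size were a mm difference, and the two issues should be kept apart.

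**Conclusion.** The concern holds, and the missing primary visit and model is its main part. If the regression at either visit can carry the claim, the two-sided false-positive chance is about 9.5%, with an upper bound of 10%, against the stated 5%. The ceiling is about 13-15% if the two ANOVA tests can carry it too. These figures rest on 19 per arm, visit correlations of 0.3 to 0.7, baseline as the only covariate and complete data. They describe what the plan permits and do not show that a selective choice will be made.

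The effect-size point is secondary and needs no SD: a measure without sign or units cannot be compared with 20 mm. The eta squared values above are illustrations, since the SD is not in the documents.

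A reader might go further and say that the ANOVA dilutes a constant 20 mm effect, (0 + 20 + 20)/3 = 13.3 mm, or that it cannot tell a sustained benefit from one lost by week 18. The first holds only if baseline is a time level, and the second only if the group-by-time test is also univariate. Section 10 settles neither, so the conclusion does not rest on them.

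This should be corrected before analysis. The planned data and an already listed model can answer the question once the plan commits to them.

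**What to change.** In Section 7.1, name one visit, 6 or 18 weeks, as primary for VAS-R. The choice is the sponsor's: week 6 addresses the effect at the end of the programme, week 18 the sustained effect. It must be fixed before the outcome data are examined by group. State in Section 8 that the 20 mm refers to that visit.

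In Section 10, name the baseline-adjusted linear regression with treatment group as a term, or an equivalent mixed model of the 6- and 18-week values, as the single primary analysis at that visit. Report the adjusted between-group difference in mm with its 95% CI, pooled over the planned imputations by Rubin's rules and read against 20 mm. Label the other visit, the repeated measures ANOVA and partial eta squared as supplementary, and say whether baseline is a time level or a covariate in the ANOVA.

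The cost is wording only: no new participants, visits or measurements, and the regression is already planned. The price is that the other visit and the ANOVA can no longer carry the primary claim.
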